4.5.1.1. Adverse Events of Special Interest

There are no adverse events of special interest identified for this study.

4.5.1.2. COVID-19 Assessment and COVID-19 AEs

A standardized MedDRA Query (SMQ) will be used to identify all COVID-19 AEs.

The incidence of AEs and SAEs of COVID-19, COVID-19 AEs leading to study intervention discontinuation, COVID-19 AEs leading to study withdrawal, and severe COVID-19 AEs at individual PT level can be obtained from the standard AE/SAE summaries.

COVID-19 assessments for participants with COVID-19 AEs will be summarized.

If >25% participants in any given cohort report ≥ 1 COVID-19 AE, then onset and duration of the first occurrence of COVID-19 AEs, and COVID-19 AE symptoms (from the COVID-19 eCRF page) will be summarized. The same rule will apply to COVID-19 SAEs.

4.5.2. Additional Safety Assessments

4.5.2.1. Laboratory Data

Summaries of worst-case changes from baseline with respect to Potential Clinical Importance (PCI) Criteria will be generated. Decreases to low, changes to normal or no changes from baseline, and increases to high will be summarized for the worst-case post-baseline. If a subject has a decrease to low and an increase to high during the same time interval, then the subject is counted in both the “Decrease to Low” categories and the “Increase to High” categories.

Separate summary tables for haematology, and chemistry laboratory tests will be produced. Liver function laboratory tests will be included with chemistry lab tests.

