AE= adverse event; ECG= Electrocardiogram, SC = subcutaneous; PD = pharmacodynamics, PK= pharmacokinetics; SAE= serious adverse event, TE = Target engagement

* Visits optional for Chinese and Japanese participants

^a ± 2hrs

^b ± 1 day

^c ± 4 day

- 1 Early withdrawal
- 2 Re-check clinical status before dose of study medication
- 3 Prior to dosing
- 4 pre-dose and 60 mins post start of SC injections
- 5 pre-dose, 30 mins, 1h, 2h, 3h & 4 h post start of SC injections
- 6 NT-pro BNP. NB: Troponin I at all time points
- 7 Result to be available prior to dose of study drug. Day -2 for PCR or rapid antigen test
- 8 Study intervention administered as 4 separate injections
- 9 Only TE sample
- 10 PK and TE blood samples taken pre-dose, 6h, 12h, 24h, 36h and 48h post start of SC injections, respectively
- 11 Blood sample to be taken pre-dose
- 12 Taken pre-dose

- The timing of planned study assessments may change during the course of the study based on emerging data/in-stream data review (e.g., to obtain data closer to the time of peak plasma concentrations) to ensure appropriate monitoring.
- Any changes in the timing of time points for any planned study assessments as the result of emerging pharmacokinetic/pharmacodynamic data from this study must be documented and approved by the relevant study team member and then archived in the sponsor and site study files but will not constitute a protocol amendment.
- The Competent Authority (CA) and ethics committee (EC) will be informed of any safety issues that constitute a substantial amendment and require alteration of the safety monitoring scheme or amendment of the informed consent form (ICF). The changes will be approved by the CA and the EC before implementation.

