Risk of Infection	
The intended pharmacologic effect of GSK3858279 may result in an CCI [REDACTED] [REDACTED]. CCI [REDACTED]
	
Participant Selection Participants with active or chronic infections or a history of recent or recurrent infections will not be included in the study – see Section 5.1.
 
Participant Monitoring Participants will be monitored for infection. Participants will be instructed in the ICF as to the signs and symptoms of infection, and to contact the site personnel should they develop.

Potential Risk of Clinical Significance	Summary of Data/Rationale for Risk	Mitigation Strategy
	CCI	
Vaccination Reactions		
Participant selection and non-permitted medications:
 
Attenuated live vaccines should not be administered to participants within 30 days prior to dosing and for five half-lives after dosing. If indicated, non-live vaccines (e.g. inactivated influenza vaccines) may be administered whilst receiving GSK3858279 based on an assessment of the benefit:risk (e.g. risk of decreased responsiveness).

Cardiac Risks		
Participant Exclusion: Participants with a history of cardiac disease or cardiac abnormalities (including abnormal Troponin I and NT-proBNP) that, in the opinion of the investigator, would compromise cardiac safety will be excluded from the study.
 
Participant monitoring: Investigations during screening include ECG,

Potential Risk of Clinical Significance	Summary of Data/Rationale for Risk	Mitigation Strategy
	CCI	echocardiogram and troponin I and NT-proBNP. Troponin I and NT-proBNP will be monitored after dosing.
Bleeding Risk	CCI	Participant exclusion and non-permitted medication Participants with a previous or current history of bleeding diathesis will be excluded.

Potential Risk of Clinical Significance	Summary of Data/Rationale for Risk	Mitigation Strategy
	CC1	Use of anti-coagulants or anti-platelet agents will be prohibited.
Skin Reactions		Participant Exclusion Participants with a history of drug-induced skin reactions and Stevens-Johnson Syndrome will be excluded. Participant Monitoring Clinically significant skin reactions will be reviewed by a dermatologist and, if appropriate, a skin biopsy will be requested for histological analysis.

Potential Risk of Clinical Significance	Summary of Data/Rationale for Risk	Mitigation Strategy

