8.2.4. Clinical Safety Laboratory Tests

- See [Appendix 2](#) for the list of clinical laboratory tests to be performed and the SoA for the timing and frequency.
- The investigator must review the laboratory report, document this review, and record any clinically significant changes occurring during the study as an AE. The laboratory reports must be filed with the source documents.
- All laboratory tests with values considered clinically significantly abnormal during participation in the study after the last dose of study intervention should be repeated until the values return to normal or baseline or are no longer considered significantly abnormal by the investigator or medical monitor.
- All protocol-required laboratory tests, as defined in Section [10.2](#), must be conducted in accordance with the laboratory manual and the SoA (Section [1.3](#)). If laboratory values from non-protocol specified laboratory tests performed at the institution's local laboratory require a change in participant management or are considered clinically significant by the investigator (e.g., SAE or AE or dose modification), then the results must be recorded.

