10.2. Appendix 2: Clinical Laboratory Tests

- The tests detailed in [Table 2](#) will be performed by the local laboratory.
- Protocol-specific requirements for inclusion or exclusion of participants are detailed in Section [5](#) of the protocol.
- Additional tests may be performed at any time during the study as determined necessary by the investigator or required by local regulations.

Table 2 Protocol-required Clinical Safety Laboratory Tests

Laboratory Assessments	Parameters				
Hematology	Platelet count	RBC Indices: MCV MCH %Reticulocytes		WBC count with differential: Neutrophils Lymphocytes Monocytes Eosinophils Basophils	
	RBC count				
	Hemoglobin				
	Hematocrit				
Clinical Chemistry ¹	Urea	Potassium	Aspartate aminotransferase (AST)/ Serum Glutamic-Oxaloacetic Transaminase (SGOT)	Total and direct bilirubin	
	Creatinine	Sodium	Alanine aminotransferase (ALT)/ Serum Glutamic-Pyruvic Transaminase (SGPT)	Total protein	
	Glucose non-fasting	Calcium	Alkaline phosphatase ²		
Routine Urinalysis	
 • Specific gravity • pH, glucose, protein, blood, ketones, bilirubin, urobilinogen, nitrite, leukocyte esterase by dipstick • Microscopic examination (if blood or protein is abnormal) 				

Laboratory Assessments	Parameters
Other Screening Tests	
 • Follicle-stimulating hormone (as needed in women of nonchildbearing potential only) • Breath Alcohol test • Urine drug screen (to include at minimum: amphetamines, barbiturates, cocaine, opiates, cannabinoids and benzodiazepines) • HIV antibody, hepatitis B surface antigen [HBsAg], hepatitis B core antibody [HbcAb] and hepatitis C virus antibody. • QuantiFERON test • Urine albumin-creatinine ratio (UACR) • Complement C3 and C4 • ³SARS-CoV2 PCR or rapid antigen test 
The results of each test must be entered into the medical notes

Other Screening and Follow-Up Tests	
 • Troponin-I (high sensitivity) • NT-proBNP

NOTES:

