10.8. Amendment History

The Protocol Amendment Summary of Changes Table for the current amendment is located directly before the Table of Contents (TOC).

Amendment 1 11-JAN-2022

Overall Rationale for the Amendment:

This is a protocol amendment with changes to the inclusion/exclusion criteria, assessment time points, clarification regarding consent to further research, clarification regarding alcohol consumption and tobacco use, changes to the protocol title to align with eTrack and correction of typographical errors. These amendments were made following feedback from the study site and HREC.

Section # and Name	Description of Change	Brief Rationale
Global Change	Troponin-T updated to Troponin I" throughout protocol	Troponin T and Troponin I have similar diagnostic accuracy.
1.1 Overall Design	Updated text – 'To try to eliminate any time dependant variability among ethnic groups, we will aim to treat Caucasian and Asian groups concurrently.	This amendment was made for clarification
1.3 Schedule of Activities	Estradiol removed from screening period table	FSH is sufficient to confirm menopause as specified in Section 10.4
1.3 Schedule of Activities	CCI [REDACTED] [REDACTED]	Aid with participant compliance to the study schedule.
1.3 Schedule of Activities	Outpatient visit removed from Day -1.	Error in original protocol. Participants will be admitted on Day -1 for an overnight stay.
1.3 Schedule of Activities	Footnotes 4 and 5 removed from Day -1 12 Lead ECG and Vital signs tests	These were present in error in the original protocol.
1.3 Schedule of Activities	COVID PCR, footnote 7 removed from Day 57, CCI and Early Withdrawal visits.	Error in original protocol, footnote applies to Day -2 visit only
1.3 Schedule of Activities - PD	Footnote 10 removed from Day 1 for Serum/Plasma for protein and PD for transcriptomic analysis.	Error in original protocol, footnote 10 applies to PK and TE samples only.
5.1 Inclusion Criteria	Inclusion Criteria #5 Updated to widen the BMI range for Caucasian participants	This amendment was made to maximise the Caucasian participant pool.
5.2 Exclusion Criteria	Exclusion Criterion #12. Typographical error Bazett's" formula is shown as QTcF in protocol, this has been corrected to QTcB	This amendment was made to correct typographical errors.

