4.2.2. Safety

The following primary safety endpoints will be summarised descriptively by ethnic cohort and treatment group, as described in Section 4.5:

- Incidence of adverse events (AEs)
- Serious adverse events (SAEs)
- Withdrawals due to AEs

- Occurrence of clinically important changes from baseline in clinical laboratory parameters, vital signs and ECGs

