6.2.1.2. Laboratory Values

Haematology				
Laboratory Parameter	Units	Category	Clinical Concern Range	
			Low Flag (< x)	High Flag (>x)
Hematocrit	Ratio of 1	Male	0.39	0.54
		Female	0.35	0.49
		Δ from BL	↓ 0.075	
Hemoglobin	g/L	Male	124	180
		Female	109	180
		Δ from BL	↓ 25	
Lymphocytes	x10 ⁹ / L		0.75	
Neutrophil Count	x10 ⁹ / L		1.5	
Platelet Count	x10 ⁹ / L		100	550
White Blood Cell Count (WBC)	x10 ⁹ / L		2.5	20

Clinical Chemistry				
Laboratory Parameter	Units	Category	Clinical Concern Range	
			Low Flag (< x)	High Flag (>x)
Albumin	g/L		30	
Calcium	mmol/L		2	2.75
Creatinine	umol/L			1.3 X ULN
Creatinine	umol/L	Δ from BL		↑ 44.2
Glucose	mmol/L		3	9
Potassium	mmol/L		3	5.5
Sodium	mmol/L		130	150
Total CO ₂	mmol/L		18	32
Creatinine Kinase	mg/dL			>1.6 X ULN
C-reactive Protein	mg/L			≥ 3.0
Troponin T	ng/ml			14.1
NT-pro BNP	ng/L			125.99

Urinalysis	
A subject is considered to have urinalysis results of PCI, if they have abnormal microscopic examination.	

Liver Function			
Test Analyte	Units	Category	Clinical Concern Range
ALT/SGPT	IU/L	High	$\geq 2 \times \text{ULN}$
AST/SGOT	IU/L	High	$\geq 2 \times \text{ULN}$
AlkPhos	IU/L	High	$\geq 2 \times \text{ULN}$
T Bilirubin	$\mu\text{mol/L}$	High	$\geq 1.5 \times \text{ULN}$
T. Bilirubin + ALT	$\mu\text{mol/L}$ IU/L	High	ALT $\geq 3 \times \text{ULN}$ AND bilirubin $\geq 1.5 \times \text{ULN}$

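### The SAP's only troponin criterion is for Troponin T, but the protocol measures Troponin I, so the troponin actually collected has no criterion of its own in the worst-case laboratory summary

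*SAP*

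**What the plan says.** SAP 4.2.2 lists among the primary safety endpoints: "Occurrence of clinically important changes from baseline in clinical laboratory parameters, vital signs and ECGs". For laboratory data, SAP 4.5.2.1 implements this as follows: "Summaries of worst-case changes from baseline with respect to Potential Clinical Importance (PCI) Criteria will be generated". It is the only laboratory summary that section describes.

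The limits are in the Clinical Chemistry table of SAP 6.2.1.2. Its two cardiac rows read "Troponin T ng/ml 14.1 NT-pro BNP ng/L 125.99", with both values in the high-flag column. The readable SAP text does not mention Troponin I.

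The protocol names a different troponin:

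- Section 1.3, Schedule of Activities, footnote 6: "NT-pro BNP. NB: Troponin I at all time points".
- Section 2.3.1, mitigation for cardiac risks: "Troponin I and NT-proBNP will be monitored after dosing".
- Appendix 2, Table 2, tests done at screening and follow-up: "Troponin-I (high sensitivity".

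Exclusion criterion 31 refers to cardiac troponin without giving the form. No current protocol procedure calls for Troponin T.

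**The concern.** Not every analyte needs a potential-clinical-importance (PCI) limit; urea and total protein, for example, have none, and that is no error. Here the SAP did decide to flag troponin, but the row is attached to an assay that is not run. The marker collected after dosing for a named cardiac risk is left without a matching criterion.

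A programmer following the SAP could omit Troponin I, apply the Troponin T limit to it, or choose a limit once the data are in hand. The first two could mis-state the number of participants with a clinically important troponin change, in either direction. The third would set a threshold after the fact. SAP 4.7.1 and 4.7.2 provide for unblinded safety data going to regulators, so the choice should be settled beforehand.

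**Working it through.** No statistical calculation is involved. The check compares current text with current text, followed by simple counts.

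**1. Analyte by location**

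| Location | Troponin named |
|---|---|
| SAP 6.2.1.2, Clinical Chemistry | T, ng/ml, flag > 14.1 |
| Protocol 1.3, SoA footnote 6 | I |
| Protocol 2.3.1, cardiac risks | I |
| Protocol Appendix 2, Table 2 | I, high sensitivity |
| Protocol 5.2, exclusion 31 | form not given |

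The SAP has one Troponin T row and no Troponin I row. The protocol schedules Troponin I and no Troponin T.

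**2. Is it a declared departure?** No. The SAP version history gives Protocol Amendment 02 (29 April 2022) as the basis for both SAP versions. SAP 4.8, which lists changes from the protocol, does not mention troponin.

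**3. How it arose.** Protocol 10.8 records that Amendment 1 (11 January 2022) changed Troponin T to Troponin I throughout. The SAP was approved on 10 May 2022, 20 + 28 + 31 + 30 + 10 = 119 days later. It was amended on 28 November 2022, a further 202 days on (119 + 202 = 321). This explains the origin only; the contradiction rests on the current texts in step 1.

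**4. Does the limit carry over?** Neither document says so. The reason given for the switch is "Troponin T and Troponin I have similar diagnostic accuracy", which is a statement about diagnostic performance and not about a shared cut-off. Appendix 2 assigns these tests to the local laboratory, so the applicable limit depends on the assay used there.

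**5. Is the row an isolated slip?** The SAP Clinical Chemistry table has 11 distinct analytes. Six are in protocol Table 2: calcium, creatinine, glucose, potassium, sodium and NT-proBNP. Five are not: albumin, total CO2, creatine kinase (printed as creatinine kinase), C-reactive protein and Troponin T. That is 5/11 = 45%. If the four liver analytes are added, because SAP 4.5.2.1 groups them with chemistry, it is 5/15 = 33%. On either count the table was not aligned with the protocol's test list. The other four are surplus rows; only the troponin row leaves a collected marker without its criterion.

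**6. Participants affected.** Three cohorts of about 10, randomised 7:3, give 3 × 7 = 21 active and 3 × 3 = 9 placebo, about 30 in total.

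**The case against.** The strongest reply is that this is one stale label in a descriptive table. No hypothesis is tested and the PK analysis is untouched. A programmer would notice as soon as the Troponin T row matched no data. Safety does not depend on the table either. Under protocol 8.2.4, "The investigator must review the laboratory report, document this review, and record any clinically significant changes occurring during the study as an AE"; the study halt rule in protocol 7.2 applies regardless; SAP 4.7.1 provides individual-level data; and NT-proBNP is flagged correctly. The full output list is in a separate document (the OPS), so the exact effect on the interim tables cannot be seen from here. The day counts and the share of unmatched rows show how the slip arose, not how much harm it does.

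Most of this stands and limits the point to tabulation. It does not remove the error. Noticing that the row matches nothing does not tell the programmer which limit to use, and neither document supplies one. Misclassification is a possibility and cannot be quantified, because the documents give no Troponin I limit, reporting unit or distribution.

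**Conclusion.** The concern holds and should be fixed. The SAP's one troponin criterion names an assay the current protocol does not schedule, and the scheduled assay has no criterion. The error is confined to one row, but that row belongs to the only laboratory summary described in SAP 4.5.2.1, which serves a primary safety endpoint.

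Confidence in the mismatch is high. How far it would alter any reported count is unknown. No unit error is claimed: the laboratory's reporting unit is not given, so ng/ml is something to verify. The conclusion assumes that the OPS and the laboratory documents, which were not available, do not already correct the row.

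**What to change.** Replace the Troponin T row in SAP 6.2.1.2 with Troponin I (high sensitivity). The sponsor should reconcile the limit and unit with the local laboratory's assay, for example by expressing the limit relative to that laboratory's upper reference limit, and record the result before any unblinded analysis. No numerical limit is proposed here. In the same pass, check the four other chemistry rows that have no counterpart in protocol Table 2, and keep or remove each one deliberately.

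The cost is one edited row with its derivation and a check of four others. No new samples, visits or tests are needed.

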3. OBJECTIVES AND ENDPOINTS

Objectives	Endpoints
Primary	

 To evaluate the safety and tolerability of a single SC dose of GSK3858279 compared with placebo administered to healthy participants including cohorts of Japanese, Chinese and Caucasians 	
 Incidence of adverse events (AEs), serious adverse events (SAEs), withdrawals due to AEs Occurrence of clinically important changes from baseline in clinical laboratory parameters (haematology, clinical chemistry, urinalysis), vital signs (blood pressure, heart rate, body temperature), and cardiac parameters (electrocardiogram)

 To assess the pharmacokinetic (serum PK) profile up to 56 days following a single SC dose of GSK3858279 in healthy participants including cohorts of Japanese, Chinese and Caucasians 	
 PK parameters: area under the concentration-time curve (AUC(0-56), AUC(0-t) post-dose), time of occurrence of last quantifiable concentration (tlast), maximum observed concentration (Cmax), and time of occurrence of Cmax (tmax) per cohort as data permits
Secondary	

 To evaluate target engagement (TE) up to 56 days following a single SC dose of GSK3858279 in healthy participants including cohorts of Japanese, Chinese and Caucasians. 	
 Reduction (%) from baseline in free CCL17: maximum, minimum and at Days 7, 14, 28 and 56, post-dose Total CCL17 (free and when bound to GSK3858279): maximum observed concentration (Cmax), time of Cmax (tmax), maximum fold increase compared to baseline, fold increase compared to baseline at Days 7, 14, 28 and 56, post-dose.

 To assess the potential for anti-drug antibody (ADA) formation 	
 Incidence of pre-existing ADAs Incidence of treatment-emergent ADAs over time (and whether neutralising)
Exploratory	
CCI	

Objectives	Endpoints
CCI	

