9.2.3. Primary Endpoint(s)

The following primary safety endpoints will be summarised descriptively by treatment group and cohort: the incidence of adverse events (AEs), serious adverse events (SAEs), withdrawals due to AEs, change from baseline in clinical laboratory parameters, vital signs, and cardiac parameters.

Categorical data will be summarised with the number and percentage of participants in each category. Continuous data will be summarised with n, mean, standard deviation (SD), median, minimum and maximum.

Primary analysis will be performed on the PK parameters AUC (0-56) post-dose and Cmax. The parameters will be \log_e transformed and then analysed using a mixed model, with ethnicity and body weight included as covariates. Geometric mean and 90% confidence intervals will be calculated for each of the ethnic cohorts, along with the comparisons for Japanese/Caucasians and Chinese/Caucasians.

All other PK parameters will be summarised descriptively, with further details to be provided in the SAP.

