4.5.2.2. Vital Signs

A summary of change from baseline vital sign values will be provided by visit and treatment group, including systolic blood pressure, diastolic blood pressure, heart rate and temperature.

Summaries of vital sign results relative to PCI criteria will also be provided. The summary will include baseline, planned visit and worst-case post baseline.

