4.8. Changes to Protocol Defined Analyses

The protocol specified that interim analysis details, including what data will be reviewed, the level of unblinding and who will have access to the data, would be documented in an interim charter. This information has been included in Section 4.7 and a separate interim analysis charter will not be produced.

Changes from the originally planned statistical analysis specified in the protocol are detailed in [Table 2](#)

Table 2 Changes to Protocol Defined Analysis Plan

Protocol Defined Analysis	SAP Defined Analysis	Rationale for Changes
Section 9.2.3: “Primary analysis will be performed on the PK parameters AUC (0-56) post-dose and Cmax. The parameters will be \log_e transformed and then analysed using a mixed model, with ethnicity and body weight included as covariates. Geometric mean and 90% confidence intervals will be calculated for each of the ethnic cohorts, along with the comparisons for Japanese/Caucasians and Chinese/Caucasians.”	Section 4.2.1.2: “The PK parameters will be \log_e transformed and analysed using a mixed model. Terms fitted in the model will include ethnicity and $\log_e(\text{body weight})$. An additional model including the ethnicity term only will be fitted.”	
 • Inclusion of additional analysis without body weight to be presented alongside the original model • Inclusion of $\log_e(\text{bodyweight})$ instead of bodyweight as linear relationship expected between PK parameters and \log_e (bodyweight)

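### SAP 4.5.2.1 omits, without declaring it, the laboratory change-from-baseline summary that protocol 9.2.3 calls for, and plans no table for the urinalysis criterion

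*SAP*

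**What the plan says.** Protocol 9.2.3 includes "change from baseline in clinical laboratory parameters, vital signs, and cardiac parameters" among the primary safety endpoints to be summarised by treatment group and cohort, and adds: "Continuous data will be summarised with n, mean, standard deviation (SD), median, minimum and maximum". The objectives table (protocol section 3, repeated in SAP 1.1) words the endpoint differently: "Occurrence of clinically important changes from baseline in clinical laboratory parameters (haematology, clinical chemistry, urinalysis), vital signs" and cardiac parameters.

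SAP 4.2.2 refers to SAP 4.5 for the safety summaries. On laboratory data, SAP 4.5.2.1 states "Summaries of worst-case changes from baseline with respect to Potential Clinical Importance (PCI) Criteria will be generated" and "Separate summary tables for haematology, and chemistry laboratory tests will be produced". It mentions neither a by-visit change summary nor urinalysis. On vital signs, SAP 4.5.2.2 states "A summary of change from baseline vital sign values will be provided by visit and treatment group". SAP 4.5.2.3 likewise keeps change from baseline by visit for ECG.

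SAP 4.8 opens its table with "Changes from the originally planned statistical analysis specified in the protocol are detailed in" Table 2. The section covers the interim charter and the PK model, and has no laboratory entry.

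**The concern.** One protocol sentence names three kinds of safety data for a change-from-baseline summary. The SAP carries out two of them and leaves out the third without saying so. Anyone programming from the SAP would produce laboratory tables that count participants crossing fixed limits, with no mean or median change at any visit. Analytes without a limit would appear in no planned laboratory summary, and the urinalysis rule would be defined but unused.

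This matters because each cohort has about 7 active and 3 placebo participants, and limits set for individual clinical concern respond poorly to a moderate shift shared by the group. Protocol 2.3.1 names immune-complex, infection and bleeding risks, for which urine findings, white-cell subsets and platelets are relevant. The Day 57 safety package, produced as SAP 4.5 describes, goes to regulators to support Chinese and Japanese participation in phase 2.

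**Working it through.** The documents state no coverage or detection figure, so there is none to reproduce.

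**1. Side by side**

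| Data type | Change from baseline in protocol 9.2.3 | Change-from-baseline summary by visit in SAP | PCI criteria in SAP 6.2.1 | Table planned against PCI |
|---|---|---|---|---|
| Vital signs | Yes | Yes (4.5.2.2) | Yes | Yes |
| ECG | Yes | Yes (4.5.2.3) | Yes | QTc categories |
| Haematology, chemistry | Yes | No | Some analytes | Yes (4.5.2.1) |
| Urinalysis | Yes, as a laboratory parameter | No | Yes, abnormal microscopy | None named |

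**2. Analytes with a PCI limit** (protocol Table 2 against SAP 6.2.1.2)

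- Haematology: 6 of 13 (haematocrit, haemoglobin, lymphocytes, neutrophils, platelets, white cells). The protocol requires "WBC count with differential: Neutrophils Lymphocytes Monocytes Eosinophils Basophils", but monocytes, eosinophils and basophils have no limit. Nor do red cell count, MCV, MCH and reticulocytes.
- Chemistry and liver: 9 of 12 (calcium, creatinine, glucose, potassium, sodium, ALT, AST, alkaline phosphatase, total bilirubin). Urea, direct bilirubin and total protein have none.
- Total: 6 + 9 = 15 of 13 + 12 = 25, or 60%.
- With troponin I and NT-proBNP, which are also measured after dosing, the count is 16 of 27 (59%), or 17 of 27 (63%) if the SAP's troponin T limit is taken to stand for the protocol's troponin I.

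**3. What a PCI table would show: platelet example**

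From the documents: 7 active participants per cohort (21 over three cohorts); low limit < 100 ×10⁹/L (SAP 6.2.1.2); worst post-baseline value used (SAP 4.5.2.1); six post-dose laboratory days with visible dates in the schedule of activities (2, 3, 8, 15, 22, 29).

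Assumed, because the documents give no values: mean 250, SD 50 between single readings, SD of change 20 to 30, and the same sustained fall in every active participant.

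Within-person SD: w = SD of change / √2 = 14.1 to 21.2. Between-person SD: b = √(50² − w²) = 48.0 to 45.3. A participant with true post-dose level x is not flagged over six visits with probability Φ((x − 100)/w)⁶. Averaging over x ~ N(250 − fall, b²) gives p₀, and P(0 of n flagged) = p₀ⁿ.

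| Fall | SD of change | 1 − p₀ | 0 of 7 flagged | 0 of 21 flagged |
|---|---|---|---|---|
| 50 | 20 | 4.64% | 0.9536⁷ = 72% | 0.9536²¹ = 37% |
| 50 | 30 | 6.13% | 0.9387⁷ = 64% | 0.9387²¹ = 27% |
| 25 | 20 | 1.42% | 0.9858⁷ = 91% | 0.9858²¹ = 74% |
| 25 | 30 | 1.92% | 0.9808⁷ = 87% | 0.9808²¹ = 67% |

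**4. What mean change at one visit would show, against placebo**

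SE = SD of change × √(1/n active + 1/n placebo).

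- One cohort, 7 against 3: 20 × 0.690 = 13.8; 30 × 0.690 = 20.7. A fall of 50 is 3.6 to 2.4 SE; a fall of 25 is 1.8 to 1.2 SE.
- Pooled, 21 against 9: 20 × 0.398 = 8.0; 30 × 0.398 = 12.0. A fall of 50 is 6.3 to 4.2 SE; a fall of 25 is 3.1 to 2.1 SE.

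**The case against.** The strongest reply is that the endpoint itself is intact. Both objectives tables define it as the occurrence of clinically important changes, and a worst-case PCI count measures that directly. Protocol 9.2.3 paraphrases the endpoint, and protocol section 9 leaves full detail to the SAP. This stands for the analytes with limits. A reader might infer that a primary endpoint has been dropped, and the documents do not support that. What is missing is a descriptive summary named in 9.2.3, where the protocol's two wordings differ. The reply does not cover urinalysis, which is named in the endpoint and has no planned table under either wording.

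A reader might also infer that ten analytes are never summarised and that urinalysis is ignored. That goes too far:

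- SAP 4.7.1 and 4.7.2 leave the interim output lists to the OPS, which is not available here.
- Protocol 8.2.4 has clinically significant laboratory changes recorded as AEs, and these are tabulated.
- A urinalysis PCI criterion does exist.

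However, SAP 4.7.1 says the Day 57 safety analysis follows SAP 4.5, and the general conventions in SAP 4.1.1 and 6.2.4 describe how tables look without creating one.

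Finally, a reader might infer that PCI tables detect almost nothing. Platelets have a distant limit. Haemoglobin, haematocrit and creatinine have limits on change, and neutrophils, lymphocytes and white cells have limits too. A single-visit tail probability would overstate the point: for a fall of 50 it gives 0.9772²¹ = 62% for none of 21, against 27–37% under the SAP's worst-case rule. With about 11 visits the figure is 18–30%. A standard error from the active arm alone would likewise overstate the case for mean change, because the objective is a comparison with placebo. At 1.2–1.8 SE, a fall of 25 in one cohort would not stand out among many analytes and visits.

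**Conclusion.** The point holds as a conflict between protocol and SAP. The laboratory change-from-baseline summary in protocol 9.2.3 is absent from SAP 4.5.2.1 and not declared in SAP 4.8. The remaining PCI summary has limits for 15 of 25 haematology and chemistry analytes (16 or 17 of 27 with the cardiac markers), and no planned table uses the urinalysis criterion. These findings rest on the text alone, subject to what the OPS may contain.

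The size of the consequence rests on the assumed platelet values and on a uniform, sustained shift. On those, a fall of 50 usually flags nobody in a single cohort, but is more likely than not to flag someone among all 21 active participants. Mean change shows that fall clearly, most of all when pooled, although SAP 4.5 presents safety data by cohort and treatment group and names no pooled table. For a fall of 25, the PCI table usually shows nothing even over 21, and mean change is informative only when pooled. The omission reduces what the study can show about moderate laboratory shifts. It does not leave the primary safety endpoint unanalysed.

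**What to change.** In SAP 4.5.2.1:

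- Add by-visit summaries of observed values and change from baseline (n, mean, SD, median, minimum, maximum), by cohort and treatment group, for every haematology and chemistry analyte in protocol Table 2, plus troponin I and NT-proBNP.
- Add a urinalysis summary that applies the existing microscopy criterion and shows shifts from baseline in dipstick protein and blood.
- Keep the PCI tables.

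Reconcile the SAP's troponin T row with the protocol's troponin I. If the sponsor decides against any of these summaries, SAP 4.8 should record the departure from protocol 9.2.3 and the reason.

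The cost is SAP wording and extra standard tables. The data are already collected, and no protocol amendment is needed.
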